6 STUDY SETTING

Data will be collected through the National Immunization Management Service (NIMS) system. NIMS will pull data from different sources, including 119 and the NHS official vaccination booking website. Details of the data flow is illustrated in the figure below:

7 SAMPLE AND RECRUITMENT

7.1 Eligibility Criteria

Participants will be adults aged between 40 and 49 residing in England who are eligible to get an NHS COVID-19 vaccine and who haven't been invited by the National Immunisation Management Service (NIMS) system.

7.1.1 Inclusion criteria

- Registered in the NHSEI system with a mobile phone number;

- Aged between 40-49 (particularly those between 40 to 44) who are eligible for COVID-19 vaccination;

- Haven't received an NHS COVID-19 SMS invitation via the national immunisation management service system.

EXTENSION

- Aged between 18-29 (most likely 29-26) who are eligible for COVID-19 vaccination;

- Registered in the NHSEI system with a mobile phone number;

- Haven't received an NHS COVID-19 SMS invitation via the national immunisation management service system.

7.1.2 Exclusion criteria

- Adults not in the specified age band or not a resident in England;

- Adults residing in England who have already received or been invited for the NHS COVID-19 vaccine via the national immunisation management service system;

- Adults residing in England who have not registered with the NHS or are not reachable by the NHS via SMS.

7.2 Sampling

7.2.1 Size of sample

Estimated size of the 40 - 49 years old cohort (data source: NIMS):

- 5.44 million in total
- 544,000 per year group

Expected **sample size** for this study:

- We expect to send the SMS invitations to 3 year groups (42, 43, 44), i.e. 1.63 million participants in total
- The actual sample size will depend on vaccine supply and vaccination capacity

EXTENSION

Estimated size of the 18 - 29 years old cohort (data source: NIMS):

- 8 million in total
- 670,000 per year group

Expected **sample size** for this study:

- We expect to send the SMS invitations to 4 year groups (26, 27, 28, 29), i.e. 2.88 million participants in total
- The actual sample size will depend on vaccine supply and vaccination capacity

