4.1 Objectives

Primary Objective:

The primary objective of this study is to identify which BI-informed text messages are effective in increasing the likelihood of booking a COVID-19 vaccination appointment and receiving first-dose vaccination among the younger cohort in England (aged 40~44).

Secondary Objective:

The secondary objective of this study is to examine the primary objective by ethnicity groups.

EXTENSION

Primary Objective:

The primary objective of this study is to identify which BI-informed text messages are effective in increasing the likelihood of booking a COVID-19 vaccination appointment and receiving first-dose vaccination among the individuals in England aged 18~29.

Secondary Objective:

The secondary objective of this study is to rule out a backfire effect of BI-informed messages (compared to control) among ethnic minority groups.

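### The extension's sample size of 2.88 million does not follow from the protocol's own inputs, which give 2.68 million

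*Protocol*

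**What the plan says.** Section 7.2.1 of the protocol builds each expected sample from a cohort size, a size per year group and a number of year groups.

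- **Main trial:** a cohort of 5.44 million aged 40 to 49, "544,000 per year group", and then "We expect to send the SMS invitations to 3 year groups (42, 43, 44), i.e. 1.63 million participants in total".
- **Extension:** a cohort aged 18 to 29 of "8 million in total", "670,000 per year group", and then "We expect to send the SMS invitations to 4 year groups (26, 27, 28, 29), i.e. 2.88 million participants in total".

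The Study Summary repeats 2.88 million as the extension's planned sample size. The extension's inclusion criterion in section 7.1.1 gives the same expected ages: "Aged between 18-29 (most likely 29-26) who are eligible for COVID-19 vaccination". Section 7.2.1 adds a caveat to both parts: "The actual sample size will depend on vaccine supply and vaccination capacity". Section 5.1 describes the extension as a 7-arm trial. The protocol gives no separate sizes for ages 26, 27, 28 and 29.

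**The concern.** The extension's total is introduced as the consequence of having four year groups, directly below a figure for the size of one year group. A reader who multiplies the two does not get the stated total. Since 2.88 million is also the planned size in the Study Summary, the mismatch affects the headline figure.

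At stake is the reliability of a planning number. The size of each arm and of each ethnic subgroup scales with the total. The extension's secondary question is whether a loss of more than 2 percentage points can be ruled out within six ethnic groups, so any calculation behind that question needs one agreed total.

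**Working it through.** **Inputs** (section 7.2.1 unless stated)

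- Main trial: 544,000 per year group, 3 year groups, stated total 1.63 million.
- Extension: 8 million aged 18 to 29 (12 single-year groups), 670,000 per year group, 4 year groups, stated total 2.88 million.
- Arms in the extension: 7 (section 5.1). Equal allocation is my assumption.

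**Step 1. Check the rule on the main trial.** Sample = number of year groups x people per year group. 3 x 544,000 = 1,632,000, which is the stated 1.63 million. The per-year figure is the cohort divided by its 10 year groups: 5.44 million / 10 = 544,000.

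**Step 2. Apply the same rule to the extension.**

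- 4 x 670,000 = 2,680,000.
- From the cohort total: 8,000,000 / 12 = 666,667, and 4 x 666,667 = 2.67 million.
- Gap: 2,880,000 - 2,680,000 = 200,000. This is 7.5% of 2.68 million (6.9% of 2.88 million).

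**Step 3. Try to reach 2.88 million.**

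| Attempt | Result |
|---|---|
| 670,000 rounded from 665,000 to 675,000 | 2.66 to 2.70 million |
| 8 million rounded from 7.5 to 8.5 million, / 12 x 4 | 2.50 to 2.83 million |
| 18 to 29 miscounted as 11 year groups: 8 million / 11 = 727,273, x 4 | 2.91 million |
| Size per year group needed: 2.88 million / 4 | 720,000 |
| Number of groups of 670,000 needed: 2.88 million / 670,000 | 4.3 |

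The 8.5 million limit (708,333 per year group) and the division by 11 come within 3% of the stated total, but both contradict the stated 670,000.

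**Step 4. Effect on precision.**

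- Per arm: 2,880,000 / 7 = about 411,400; 2,680,000 / 7 = about 382,900.
- Standard errors: sqrt(2.88 / 2.68) = 1.037, so about 3.7% larger with 2.68 million.
- Detectable difference between one message and control = (1.960 + 0.842) x sqrt(2p(1-p)/n), for two-sided 5% significance and 80% power without multiplicity adjustment. The booking rate p is an assumption, because the protocol gives none.

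| Assumed p | n = 411,400 | n = 382,900 |
|---|---|---|
| 10% | 0.185 points | 0.192 points |
| 30% | 0.283 points | 0.293 points |
| 50% | 0.309 points | 0.320 points |

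**The case against.** The strongest reply is that 670,000 is an average over all twelve ages, while the sample is expected to be the four oldest. If those four average 720,000, then 2.88 million is correct. The cohort total does not exclude this: the other eight year groups would hold 8 - 2.88 = 5.12 million, or 640,000 each. This stands as a possibility. It means the protocol cannot be said to overstate the trial by 200,000; it can only be said that the total does not follow from the printed inputs. It does not remove the point, because the protocol neither gives those sizes nor says that the four ages differ from the average.

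A second reply is that this is a forecast of who will be invited, and the protocol says supply and capacity will decide the actual number. That is true, and it limits the importance of the point. But the caveat covers departures from the plan. It does not explain why the planned figure disagrees with its own inputs.

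Three stronger readings are tempting and are not supported.

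- **The wrong total set the ethnic grouping.** A reader might infer this from the note in section 4 on a preliminary power calculation. The note stands under the main trial's research question, and the main trial's total reproduces. The extension reuses the same groups, but nothing shows that 2.88 million determined them.
- **Printed subgroup numbers are wrong.** The protocol prints no per-arm, per-ethnic-group or power figures for the extension, so there are none in it to correct.
- **The objective is too wide for the sample.** Section 4.1 states the primary objective for "receiving first-dose vaccination among the individuals in England aged 18~29", while ages 26 to 29 are expected. The objective matches the eligible range of 18 to 29, and the narrower ages are openly given as likely and dependent on supply. This is no contradiction.

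**Conclusion.** The inconsistency is real. On the protocol's own inputs and by the rule that reproduces the main trial's figure, the extension's expected sample is 2.68 million, against a stated 2.88 million in section 7.2.1 and the Study Summary. That the figures do not reconcile rests on no assumption beyond the printed numbers.

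Which figure is wrong is not established. A slip of one digit in the total is plausible but cannot be shown, and an unstated larger size for ages 26 to 29 is equally open. Nor is 2.68 million shown to be the true number of participants: 670,000 is given as a cohort size, and the protocol does not say whether it already excludes people without a registered mobile number or with an earlier invitation.

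The consequence is small. With seven equal arms, the larger standard errors move the detectable difference by about 0.01 percentage points at assumed booking rates of 10% to 50%, which does not threaten the primary comparison. The point is worth correcting because a headline planning number is wrong as written and cheap to repair.

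**What to change.** In section 7.2.1 and the Study Summary, do one of two things:

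- restate the extension's expected sample as 2.68 million; or
- keep 2.88 million and state the sizes of the year groups aged 26, 27, 28 and 29 that add up to it, with their source.

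In either case, confirm which total any power calculation for the extension used, including any for the ethnic groups, and rerun it if that total changes.

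The cost is one figure in two places, or one added line of year-group sizes. The design, randomisation and analysis do not change. If the lower total is adopted, the stated size becomes slightly less favourable.

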7.2.2 Sampling technique

We will use a stratified sampling technique to select participants. Eligible participants will be stratified by age, and we will send text messages starting with older year groups and progressing to younger ones according in line with their eligibility. The rationale of the sampling strategy is that vulnerability to the coronavirus increases with age, thus older people have priority over younger people.

7.3 Recruitment

7.3.1 Sample identification

NHSEI will identify eligible participants using the NIMS system and pull the data from the National Booking System and NIMS system. SMS invitations will be sent to all eligible participants according to year group, starting with the oldest cohort eligible at the time of the study. There are no costs involved for participants to participate in this study.

7.3.2 Consent

We are not seeking consent for this trial for six reasons:

- Participants will have already consented to receive SMS communication from the NHS. However, we recognise that this consent does not imply that the patient has consented to be part of this research study.
- The intervention itself does not affect the treatment being provided to the patient by the NHS.
- Seeking informed consent could lead to observer or "Hawthorne" effects. That is, patients' knowing they are part of a trial may influence their behaviour and affect the external validity of the trial.
- Seeking informed consent could also lead to selection effects whereby those that opt into the trial may be different from the wider population of interest. This would affect the robustness of any findings, since results in the study may not be replicated in the wider patient population.
- Seeking informed consent would have added an additional burden both to participants and to the service as it would require an additional contact point to seek consent. There is also no existing way in the National Immunisation Management System (NIMS) to record this consent, therefore technical changes would have to be made by NIMS to allow this. We felt that this was an unnecessary burden for the already stretched NIMS.
- Only pseudonymised data will be transferred to BIT and NHSEI researchers for analysis.
- There are precedents for not seeking informed consent for text messaging trials. For example, an earlier trial (17/YH/0264) involving text messages interventions received NHS REC approval.

8 ETHICAL AND REGULATORY CONSIDERATIONS

The aim of the intervention is to encourage recipients to receive their COVID-19 vaccine, which will lower their risk from COVID-19. Overall we believe this will have health benefits for recipients and the risk is minimal.

Potential risks

One risk of SMS interventions is that the BI messages might not work equally well for everyone. This

may result in some groups of participants being encouraged to book a vaccine, but might inadvertently discourage some other groups from booking it. This risk has been minimised by developing the messages based on evidence available in the literature, as well as input from experts at BIT, NHS and PHE. In addition, to further minimise this risk, messages have been pre-tested using an online panel, excluding any message performing worse than the business as usual message.

Potential benefits

For participants less motivated to get a COVID-19 vaccine, the messages might motivate or simply prompt them to get one, lowering their risk of severe outcomes from COVID-19 infection. Therefore we believe this will have health benefits for participants.

Potential ethical concerns

There is an ethical issue that some patients will get messages that are more effective than others, even if there is no backfire effect. However, we cannot know in advance of the trial which message will be most effective, so ex-ante participants all have an equal chance of getting the most effective one. However, no participants will receive a text message who would not otherwise have received one and all messages will contain the same information for booking appointments. There is no additional booking burden for intervention recipients; they will simply receive a different invitation message directing them to book a vaccination appointment in the usual way.

8.1 Assessment and management of risk

One risk is that the behaviourally-informed messages have an unintended **backfire effect** and reduce vaccination uptake in some groups. This risk has been minimised by developing the messages based on the evidence available from related research, as well as input from experts at the Behavioural Insights Team (BIT), NHS England and NHS Improvement (NHSEI), and Public Health England (PHE). To further mitigate this risk, messages have been pre-tested with an online panel and messages leading to a significant decrease in intention to get vaccinated have not been included in the trial. In addition, all participants who haven't booked an appointment within two weeks will receive a reminder delivered via post, further mitigating the risk of potential message backfiring.

Mitigation strategies:

If backfire occurs for any BI message or for any ethnicity group, we propose the following mitigation strategy: **every participant** who hasn't booked an appointment will be sent the default reminder letter in **14-16 days** (the status quo being 14-21 days) after they receive the SMS invitation.

Definition of backfire: Any BI message arm whose corresponding booking rate within 72 hours is equal to or more than **2** percentage points lower (and the effect is **significant**) compared to the business-as-usual message (either for all sample or for any of the 6 specific ethnic groups). It's worth noting that if the negative effects are *not statistically significant*, or if the magnitude of negative effects is *less than 2 percentage points*, we won't classify them as backfire.

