4 RESEARCH QUESTION/AIM(S)

1. Primary research question: Which BI-informed text messages can increase the likelihood of booking a COVID-19 vaccination appointment and receiving first-dose vaccination, compared to the control text message?

2. Secondary research question: Which BI-informed text messages can increase the likelihood of booking a COVID-19 vaccination appointment and receiving first-dose vaccination **among the following specific subgroups,** compared to the control text message?

- Missing (99)
- Mixed White and any Black (D, E, M, N, P)
- "Other" ethnic group (R, S)
- White any other (C)
- Asian Indian and Mixed White and Asian or other (F, G, H)
- Pakistani, Bangladeshi and other (J, K, L)

Note. The coding and categorisation scheme of the ethnicity groups is adopted from the NIMS system. The number and categorisation of specific subgroups was decided by preliminary power calculation based on expected sample size. A more granular ethnicity breakdown than the one described here would require a larger sample size.

EXTENSION

1. Primary research question: Which BI-informed text messages can increase the likelihood of booking a COVID-19 vaccination appointment and receiving first-dose vaccination, compared to the

control text message?

2. Secondary research question: Can we rule out that BI-informed text messages backfire (decrease by more than 2 percentage points the likelihood of booking a COVID-19 vaccination appointment and receiving first-dose vaccination) **among the following specific subgroups,** compared to the control text message?

- Missing (99)
- Mixed White and any Black (D, E, M, N, P)
- "Other" ethnic group (R, S)
- White any other (C)
- Asian Indian and Mixed White and Asian or other (F, G, H)
- Pakistani, Bangladeshi and other (J, K, L)

Note. See section 8.1 for a more detailed definition of backfire.

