4.2 Outcome

Primary outcome: whether participants book a COVID-19 vaccination appointment (either online or by calling 119) within 72 hours of receiving the SMS invitation. This is a binary outcome, i.e. the booking status will be coded as 1 if the participant makes the booking within the time frame, and coded as 0 if they don't.

Secondary outcome: whether participants receive their first-dose vaccination within 14 days of receiving the SMS invitation. This is also a binary outcome, i.e. the vaccination status will be coded as 1 if participants receive a COVID-19 vaccination within the time frame, and coded as 0 if they don't.

EXTENSION

Primary outcome: whether participants book a COVID-19 vaccination appointment (either online or by calling 119) within 72 hours of being sent the SMS invitation. This is a binary outcome, i.e. the booking status will be coded as 1 if the participant makes the booking within the time frame, and coded as 0 if they don't.

Secondary outcomes:

- whether participants receive their first-dose vaccination within 14 days of being sent the SMS invitation. This is also a binary outcome, i.e. the vaccination status will be coded as 1 if participants receive a COVID-19 vaccination within the time frame, and coded as 0 if they don't.
- whether participants book a COVID-19 vaccination appointment (either online or by calling 119) within 14 days of being sent the SMS invitation. This is a binary outcome, i.e. the booking status will be coded as 1 if the participant makes the booking within the time frame, and coded as 0 if they don't.

5 STUDY DESIGN AND METHODS of DATA COLLECTION AND DATA ANALYSIS

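### The extension's backfire question covers booking and first-dose vaccination, but Section 8.1 defines backfire on 72-hour booking only, so the stated rule leaves the vaccination half unanswered

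*Protocol*

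**What the plan says.** In the Protocol's Section 4 (EXTENSION), the secondary question is whether it can be ruled out that messages "decrease by more than 2 percentage points the likelihood of booking a COVID-19 vaccination appointment and receiving first-dose vaccination" in six named ethnic groups, compared with control. A note adds: "See section 8.1 for a more detailed definition of backfire". Section 4.1 (EXTENSION) gives the matching objective, to "rule out a backfire effect of BI-informed messages (compared to control) among ethnic minority groups", and names no outcome.

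Section 8.1 opens by describing the risk as messages that "reduce vaccination uptake in some groups". Its operative definition is narrower: "Any BI message arm whose corresponding booking rate within 72 hours is equal to or more than" 2 percentage points lower than the business-as-usual message, with a significant effect, in the whole sample or in any of the six ethnic groups. Of negative effects that are smaller or not significant it says "we won't classify them as backfire". A flag leads to the default reminder letter going out at 14-16 days rather than 14-21 days.

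Section 4.2 (EXTENSION) makes 72-hour booking the primary outcome. The secondary outcomes are "whether participants receive their first-dose vaccination within 14 days of being sent the SMS invitation" and, newly added, booking within 14 days. Section 5.3 fits the model to booking and vaccination within each ethnic group, with Benjamini-Hochberg adjustment at a 5% false discovery rate and each ethnicity as its own family. The extension follows the same strategy and adds 14-day booking.

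**The concern.** In the main trial, the Section 8.1 definition served risk management, and the secondary question was about effectiveness by ethnicity. The extension turned backfire into the secondary research question and tied it to the existing definition. Section 8.1 was not revised for this: it has no EXTENSION paragraph, and Appendix 1 does not list it among the updated sections.

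The question therefore names two outcomes and the rule that decides it uses one. The extension could report backfire as ruled out in an ethnic group on the booking result alone, while the same group's vaccination estimate lay beyond the stated margin. The assessment carries more weight in the extension because Section 8.1 relies on online pre-testing as a safeguard, whereas the notes to the extension messages say pre-testing was not possible and that three of the six treatment messages are new.

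**Working it through.** **No figure to reproduce.** The 2-point margin is set by statement, and the protocol gives no power figure for the backfire question. The check is a comparison of texts, followed by an illustration.

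**Side by side.**

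| Element | Section 4, EXTENSION question | Section 8.1 definition |
|---|---|---|
| Outcome | booking and first-dose vaccination | booking only |
| Time window | none given | 72 hours |
| Threshold | more than 2 points | 2 points or more |
| Groups | six ethnic groups | whole sample and six ethnic groups |
| Significance | not mentioned | required |

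The first row is the substance of the point. The third row is a smaller mismatch: a fall of exactly 2 points qualifies under Section 8.1 and not under Section 4.

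**Booking and vaccination are separate records.** The dummy data set in Section 5.2 has rows with a booking and no first dose, and a row with no booking and a first dose. These are invented rows and say nothing about frequency, but they show that the plan does not treat one outcome as implying the other.

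**Illustration.** All rates and subgroup shares are assumptions.

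- Group size: 2.88 million (Section 7.2.1) / 7 arms, assumed equal = about 411,400 per arm. Subgroup shares of 1% to 10% give 4,114 to 41,143 per arm.
- Test: z = (p_t − p_c) / √[p_c(1 − p_c)/n + p_t(1 − p_t)/n], where p_c and p_t are the control and message-arm rates. It is unadjusted and approximates the planned logistic model.

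*Vaccination falls, 72-hour booking does not.* Booking is 30% in both arms; 14-day vaccination is 40% versus 36%. The booking difference is 0, so the arm is not classed as backfire. The vaccination difference is −4 points. At n = 4,114, SE = √[(0.2400 + 0.2304)/4,114] = 0.0107 and z = −3.7. At n = 41,143, z = −11.8.

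*72-hour booking falls, 14-day outcomes do not.* Booking is 30% versus 27% at 72 hours, with 14-day booking and vaccination equal. The difference is −3 points. At n = 4,114, SE = √[(0.2100 + 0.1971)/4,114] = 0.0099 and z = −3.0. At n = 41,143, z = −9.5. The arm is classed as backfire, and only 14-day booking would help the reader judge whether the fall was delay or loss.

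**Sensitivity to sample size.** Section 7.2.1 also gives 670,000 per year group, and 4 × 670,000 = 2.68 million rather than 2.88 million. With 2.68 million, a 1% subgroup has about 3,828 per arm and the z values become −3.6 and −2.9. The classifications do not change.

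**Number of flag tests.** There are 6 messages and 7 groups (the whole sample and six ethnic groups). The rule as written has 6 × 7 = 42 tests. Adding vaccination gives 2 × 42 = 84. Adding 14-day booking as a third criterion would give 3 × 42 = 126.

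**The case against.** The 72-hour rule has a sound purpose. It can be read before the reminder letter goes out at 14-16 days, whereas 14-day vaccination is not complete in time to act on. It also uses the primary outcome. The paired wording of booking and receiving a dose appears in the primary research questions of both trials too, although their primary outcome is booking alone. This all stands, and it supports keeping the rule as a trigger. It does not make a booking-only rule an answer to a question that attaches a margin to vaccination.

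A reader might infer that a fall in vaccination could go unnoticed or could never be flagged. The documents do not support that. Section 5.3 estimates and tests vaccination for every message in every ethnic group, so a fall would be visible, and an arm that also shows a qualifying 72-hour booking fall is flagged through booking. What is missing is the classification, not the evidence.

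A reader might also infer that the rule measures only speed of booking, and that a 72-hour fall which has closed by day 14 is harmless. That goes too far as well. The protocol gives no basis for calling such a shift harmless. Fourteen-day vaccination is itself sensitive to timing: someone who books promptly for day 15 is coded 0, and Section 7.2.1 notes limits of supply and capacity.

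Finally, all messages carry the same booking information (Section 8), and nothing in the documents shows that wording alters vaccination among equal numbers of bookers. The assumed rates show what the rule does, not what is likely to happen.

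**Conclusion.** The mismatch is established from the text. The extension's secondary question puts a 2-point margin on booking and on first-dose vaccination, and the definition it relies on uses 72-hour booking only. A vaccination fall without a qualifying booking fall would be estimated but not classed as backfire, so the stated rule leaves the vaccination part of the secondary objective unanswered. The threshold is also worded in two ways.

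The size of any resulting error cannot be taken from the documents. Under the assumed rates, a 4-point vaccination fall goes unclassified in subgroups of 1% to 10%. The textual conclusion does not depend on those rates.

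This should be fixed but is not critical. The primary question, outcomes, randomisation, data and effect estimates are untouched. If the narrowing to booking was intended, Section 4 claims more than will be assessed, and the two sections still need reconciling.

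**What to change.** Reconcile Sections 4 and 8.1 with an EXTENSION paragraph:

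1. Keep the 72-hour booking rule in Section 8.1 and label it the early operational trigger.
2. State separately that the extension's conclusion on backfire also applies the 2-point margin to 14-day first-dose vaccination, for the whole sample and for each ethnic group.
3. Extend the planned Benjamini-Hochberg adjustment to these tests, and say whether they join the existing families (12 tests each instead of 6) or form their own.
4. Report 14-day booking alongside, as an aid to judging delay or loss, without making it a third flag criterion.
5. Use one threshold wording in both sections: either more than 2 points, or 2 points or more.

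No new data are needed, because all three outcomes are already collected and modelled by arm within ethnic group. The cost is wording plus a doubling of flag tests from 42 to 84, which gives more chances of a flag. Leaving 14-day booking as a descriptive aid avoids the further rise to 126.

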 - Any first-dose vaccination received within 14 days of receiving the SMS (*secondary outcome*). The vaccination status will be coded as 1 if participants receive their

vaccination within the time frame, and coded as 0 if they don't.

- X' is a vector of characteristics such as age, gender. It also includes timestamps e.g. date and time of receiving the text.
- k=1...7 are the different ethnicity subgroups. The **reference group** will be White British and Irish (A, B), and **the other subgroups** 1...6 are specified in the research question section slide).

 $\hat{\beta}_1 \dots \hat{\beta}_7$ constitute the estimated parameter of interest. In each regression, they represent the impact of BImessageX on the outcome, compared to the control SMS, for the ethnic group k considered.

P-values will be adjusted by multiple comparisons using Benjamini-Hochberg correction, treating each ethnicity as a separate family of hypothesis tests in which each arm is compared to the control with a maximum false discovery rate of 5%.

EXTENSION

The analysis will follow the same strategy of the main experiment, but it will include one additional secondary outcome - booking rate within 14 days from being sent the message.

Statistical packages

Researchers at BIT will use Rstudio1.2 & R3.6.0 and Stata 16th Edition statistical packages to analyze the results.

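### The backfire definition in section 8.1 leaves out White British and Irish, although its own trigger sentence and the section 5.3 models include that group (low severity)

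*Protocol*

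**What the plan says.** Protocol section 8.1 contains two sentences on the scope of the backfire rule. The mitigation paragraph opens with "If backfire occurs for any BI message or for any ethnicity group". The definition that follows starts "Any BI message arm whose corresponding booking rate within 72 hours is equal to or more than" 2 percentage points lower than the business-as-usual message, requires significance, and limits the check: "either for all sample or for any of the 6 specific ethnic groups". For falls that are not significant or are smaller than 2 points, it adds "we won't classify them as backfire".

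The six groups are those listed under the secondary research question in section 4: missing ethnicity, mixed White and any Black, other, any other White, Indian with mixed White and Asian, and Pakistani with Bangladeshi. Codes A and B are not in that list.

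Section 5.3 (Secondary analysis) fits the message model separately by ethnicity: "k=1...7 are the different ethnicity subgroups". The reference group "will be White British and Irish (A, B), and" the other six are those of section 4. Each ethnicity is its own Benjamini-Hochberg family.

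Section 4.1 gives the extension's secondary objective as "to rule out a backfire effect of BI-informed messages (compared to control) among ethnic minority groups".

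**The concern.** The definition is narrower than the sentence it is meant to serve and narrower than the planned analysis. White British and Irish is an ethnicity group under section 5.3, with its own model and its own corrected tests, yet a fall in that group alone cannot meet the definition.

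Its only route into the rule is the whole-sample comparison, where its effect is averaged with those of the other groups. A fall above the 2-point limit within the group can then come out below 2 points overall, and the definition says expressly that such a fall is not backfire. Two things are at stake: what the trial reports about backfire, and whether the reminder letter goes out at 14-16 days rather than 14-21. The analyst would also have to choose between two adjacent sentences after seeing the data.

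**Working it through.** **Inputs from the protocol.** Threshold: 2 points, on 72-hour booking (section 8.1). Groups: 6 listed plus 1 reference = 7, which agrees with k = 1 to 7 in section 5.3. Arms: 8 in the main trial, 7 in the extension (section 5.1). Main-trial size (section 7.2.1): 3 × 544,000 = 1,632,000, which reproduces the stated 1.63 million. Extension size: 4 × 670,000 = 2.68 million, which does not reproduce the stated 2.88 million. The smaller figure is used below, and the choice does not matter here.

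**Assumptions, not in the protocol.** The White British and Irish share w (0.4 to 0.9), the control booking rate (30%, or 10% to 50% as a range), equal allocation, and a simple difference in proportions in place of the adjusted model.

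**Dilution.** Overall effect = w × (effect in White British and Irish) + (1 − w) × (average effect in the other groups). With no effect elsewhere, the overall fall reaches 2 points only when the group's fall reaches 2/w:

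| w | Fall needed in the group (points) |
|---|---|
| 0.4 | 5.00 |
| 0.5 | 4.00 |
| 0.6 | 3.33 |
| 0.7 | 2.86 |
| 0.8 | 2.50 |
| 0.9 | 2.22 |

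At w = 0.7, a gain of 1 point elsewhere raises the limit to (2 + 0.3)/0.7 = 3.29, and a fall of 1 point elsewhere lowers it to (2 − 0.3)/0.7 = 2.43. A gap exists for any w below 1 unless the other groups also fall by 2 points or more on average.

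**Example.** Take w = 0.7, a 2.5-point fall in the group and no effect elsewhere. The overall fall is 0.7 × 2.5 = 1.75 points, which is below the threshold.

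**Is the group's fall distinguishable from chance?** SE = √(2 × 0.3 × 0.7 / n), with n per arm in the group.

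- Main trial: 1,630,000 / 8 = 203,750; × 0.7 = 142,625; SE = 0.172 points; 2.5 / 0.172 is about 15 SE.
- Extension: 2,680,000 / 7 = 382,857; × 0.7 = 268,000; SE = 0.125 points; 2.5 / 0.125 = 20 SE.

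In the main trial, over shares of 40% to 90%, n runs from 81,500 to about 183,400 per arm. The SE at its largest (50% booking) is then 0.25 down to 0.17 points. The power to find a 2-point fall significant at two-sided 0.05/7 is about 100% at every share, and at control rates of 10%, 30% and 50%.

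**What the primary analysis would show in the same example.** The overall SE is √(0.42 / 203,750) = 0.144 points in the main trial and √(0.42 / 382,857) = 0.105 in the extension. A 1.75-point fall is then about 12 and 17 SE below zero. For the overall effect to reach zero, the other groups together would have to gain 1.75 / 0.3 = 5.8 points.

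**The case against.** The strongest reply is that the restriction is deliberate. The secondary question in section 4 lists the same six groups for both the main trial and the extension, the extension's objective concerns ethnic minority groups, and the rationale in section 2 rests on hesitancy and lower uptake in particular populations. On this view the definition repeats that scope, and a defined term governs the looser phrase before it.

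This stands in part: it explains where the number six comes from, and it is a good reason to leave the extension's objective alone. It does not settle the risk rule. Sections 8 and 8.1 describe the hazard as one to some groups, without restriction. The rule already covers the whole sample, and the six groups include missing ethnicity, so it is not a minority-only rule. The main trial's secondary objective in section 4.1 is by ethnicity group without that limit.

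Two stronger readings are tempting, and the protocol supports neither. A reader might infer that the trial is blind to harm in this group. It is not: section 5.3 estimates and tests the effect there, and the group counts in the whole-sample check. A reader might also infer that a harmful message could be cleared and then recommended. No section makes recommendation depend on the backfire label. Section 1 says that the best-performing message was rolled out, and the message in the example would show a highly significant overall fall.

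It is also right that little follows in practice. Section 8.1 promises a postal reminder to everyone who has not booked within two weeks. Mitigation only narrows its window from 14-21 to 14-16 days, so the latest letter goes out at most 21 − 16 = 5 days sooner.

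**Conclusion.** The point holds, at low severity. The trigger sentence and the definition in section 8.1 differ in scope. If the definition is followed as written, a statistically clear fall of 2 points or more among White British and Irish can be reported as no backfire.

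The omission itself is plain in the text and needs no assumption. The width of the gap does: with no effect elsewhere, it runs from 2 points up to 3.33 at a 60% share but only up to 2.22 at 90%, and the protocol does not give the share. The standard errors also rest on an assumed booking rate, but the conclusion that such a fall would be clear of chance is the same across the whole range tried. The consequence is confined to the reported backfire conclusion and the timing of a letter that all non-bookers receive.

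**What to change.** Reconcile the two sentences in section 8.1 by defining backfire for the whole sample or for any of the seven ethnic groups analysed in section 5.3. Keep the extension's secondary question and objective (sections 4 and 4.1) on the six listed groups, and say that the risk rule is wider than that objective.

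The change is one phrase. It needs no new data or model, because the seventh group's estimates are already planned. It adds one more group to the check (7 message comparisons in the main trial, 6 in the extension), and so a slightly higher chance of a false flag. That chance is limited by the correction within each ethnicity and by the 2-point requirement.
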